We present descriptive statistics as median (interquartile range) for continuous variables and proportions for categorical variables. For the primary analysis, and all comparisons of categorical variables between the intervention and control group, we used the Mantel-Haenszel test, accounting for each hospital site as an individual stratum. The Mantel-Haenszel approach was used to obtain the pooled relative risks across hospital strata without adjusting for other baseline factors. As a sensitivity analysis, we used modified Poisson generalized estimating equations with a robust variance estimator to present the relative risk estimates adjusting for the following characteristics assessed at the time of randomization: age, sex, race, creatinine, blood urea nitrogen, white blood cell count, heart rate, respiratory rate, systolic and diastolic blood pressure, CHF, hypertension, diabetes, modified SOFA score, Elixhauser comorbidity score, and hospital.²⁻⁴ We used the Van Elteren test to compare continuous variables across the intervention groups, again accounting for hospital strata. To compare time-to-event between study groups, we used Cox proportional hazard regression with intervention as the independent variable, stratified by hospital, with censoring at 14-days after randomization. For individual hospital analyses, Kaplan-Meier curves were generated and log-rank tests were used. Patients discharged prior to 14 days without an outcome of interest were assumed to be free of that outcome at 14 days. Death was treated as a censoring event in analyses where death was not the outcome. We used Schoenfeld residuals to examine the proportional hazards assumption in Cox models; there were no violations.

We prespecified several secondary outcomes and subgroup analyses which we present without adjustment for multiple comparisons. We also pre-specified that each hospital would be analyzed

independently for evidence of heterogeneity of alert effects. Given the observed heterogeneity of effects, we explored mediators of that heterogeneity through the use of a generalized linear model in which the independent variables included an alert-by-hospital-type interaction term. Patient-level covariates were then added to this base model to determine if the significance of the interaction would be ablated by including these factors. Although patient characteristics did not account for the heterogeneous results, grouping hospitals into “teaching” vs. “non-teaching” did.

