Due to the unexpected finding of increased harm from the alert at non-teaching hospitals, we conducted several *post hoc* analyses, which are specifically identified in the results. To determine if the effect was mediated by actions downstream of the alert, we performed a formal mediation analysis using the method of Baron and Kenny (adjusted for age, sex, race, creatinine, blood urea nitrogen, white blood cell count, heart rate, respiratory rate, systolic and diastolic blood pressure, CHF, hypertension, diabetes, malignancy, modified SOFA score and Elixhauser comorbidity score at the time of randomization) of the following hypothesized mediators: markers of fluid overload, certain medications, the presence of renal consult, attending involvement in the care of the patient (as measured by the percent of alerts that went to attendings versus other providers), and the burden of other interruptive alerts (such as those for sepsis or medication interactions).^{5,6} The burden of other interruptive alerts was quantified as the number of other alerts received while the patient was eligible to be receiving AKI or Control alerts, divided by the amount of time they were eligible, leading to an average “non-aki alert per day” metric. Finally, we examined the rates of death and AKI progression in the time period 2 years prior to the start of the trial in each hospital to assess the degree of contamination across the study arms.

We assessed whether alert effectiveness changed over time by including an interaction term representing “time from first enrollment at this hospital” with the randomization status in a logistic regression equation. A significant p-value for this interaction term would suggest that the effect of the alert waxed or waned over time once it was “live” at a given hospital.

Our preliminary data suggested that 24.5% of patients would experience the composite outcome. We determined that a relative 20% reduction in this outcome (to 19.6) would be clinically significant. A sample size of 2,512 in each arm of the study achieves 90% power to detect this degree of change, but given the potential for contamination across study arms (whereby clinicians “learn” to identify and care for AKI over the course of the trial), which would tend to bias the results towards the null, we inflated the sample size by 20% to a total of 6,030.

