A single interim analysis was conducted at 50% enrollment to assess for benefit or harm of the alert. An independent Data and Safety Monitoring board (who were unblinded to study assignment) were given guidelines to terminate the study if the p-value associated with interim analysis was ≤ 0.001 for efficacy or ≤ 0.005 for harm. They also had the authority to terminate the study of their own accord regardless of those recommendations. They recommended the study continue at the interim assessment.

Statistical tests were conducted in Stata (v 15.1, College Station TX), SAS (v 9.4, SAS Institute, Cary, NC) and R (RStudio version 1.2.5033 (R version 3.5.3), Boston, MA) and a p-value of ≤ 0.04 was considered statistically significant for the primary outcome (to account for the interim analysis).

We do not report P-values for secondary and exploratory analyses, except in the case of safety outcomes, but report 95% confidence intervals in all cases. The widths of the 95% confidence intervals have not been adjusted for multiplicity and inferences drawn from these may not be reproducible.

Box 1

Characteristic	Hospital 1	Hospital 2	Hospital 3	Hospital 4	Hospital 5	Hospital 6
Location	Urban	Urban	Urban	Suburban	Suburban	Suburban
Bed Count	1030	511	383	206	280	60
Academic	Yes	Yes	Yes	Yes	No	No
Interns / Residents	826 (Shared)		117	23	1 (pharmacy)	0
Patients Enrolled	2515	1248	935	503	684	146
Median (IQR) SOFA Score at Randomization	2 (1 – 4)	1 (1 – 2)	2 (1 – 4)	2 (1 – 3)	2 (1 – 4)	2 (1 – 3)
Median (IQR) Elixhauser Comorbidity Score at Randomization	6 (4 – 8)	6 (4 – 8)	7 (5 – 9)	6 (4 – 8)	7 (5 – 8)	7 (5 – 8)

2. Zou G. A modified poisson regression approach to prospective studies with binary data. *Am J Epidemiol*. 2004;159(7):702-706.

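### The covariate list for the post hoc mediation analysis omits hospital, so if hospitals were pooled, site differences could be mistaken for mediation

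*SAP*

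**What the plan says.** The post hoc mediation analysis is described in the SAP, Statistical Analysis: "we performed a formal mediation analysis using the method of Baron and Kenny". The model is "adjusted for age, sex, race, creatinine, blood urea nitrogen, white blood cell count, heart rate, respiratory rate", followed by blood pressure and comorbidities, and the list closes with "diabetes, malignancy, modified SOFA score and Elixhauser comorbidity score at the time of randomization". That makes 16 covariates, all at patient level. No stratification or clustering by hospital is mentioned for this analysis, and the text does not say whether it used all six hospitals or only the non-teaching ones.

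The other between-arm analyses in the same section handle hospital explicitly:

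- Primary and other categorical comparisons: "we used the Mantel-Haenszel test, accounting for each hospital site as an individual stratum".
- Continuous variables: the Van Elteren test, again by hospital stratum.
- Time to event: "Cox proportional hazard regression with intervention as the independent variable, stratified by hospital".
- Adjusted sensitivity model: almost the same list as the mediation model, without malignancy, ending "diabetes, modified SOFA score, Elixhauser comorbidity score, and hospital".

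The hypothesised mediators are markers of fluid overload, certain medications, renal consult, the percentage of alerts that went to attendings, and the burden of other interruptive alerts. In Box 1 the row "Interns / Residents" gives 826 shared by hospitals 1 and 2, then 117, 23, 1 (pharmacy) and 0 for hospitals 3 to 6.

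**The concern.** A mediation estimate multiplies two quantities: the effect of the alert on the mediator, and the association of the mediator with outcome given the alert. Patients were randomised individually, so the first is unconfounded with or without hospital in the model. The second is observational, and its validity rests entirely on the covariates.

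Hospitals 5 and 6 have essentially no trainees, so the attending share of alerts there is very likely higher than at hospitals 1 to 4. Across six pooled hospitals, that mediator partly labels the hospital type. If hospital type also predicts outcome, the mediator coefficient picks up the difference.

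This does not require different baseline risks. If the alert does harm only at hospitals 5 and 6, those hospitals have a higher event rate averaged over the two arms, and a model with a single alert term leaves that excess for the mediator to absorb. The SAP reports that patient characteristics did not explain the heterogeneity of the alert effect but that teaching status did. The 16 patient covariates may therefore not remove the hospital signal.

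The analysis is the SAP's means of explaining an unexpected harm. A falsely identified mediator would point to the wrong mechanism.

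**Working it through.** The documents report no mediation estimate, so there is none to reproduce. The omission is established by setting the two covariate lists side by side, as above. What follows shows how large the effect could be.

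**Inputs from the documents.** Box 1 enrolment is 2515, 1248, 935, 503, 684 and 146, a sum of 6,031. Hospitals 5 and 6 contribute 830, a fraction of 830/6031 = 0.138.

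**Assumed inputs.** Attending share is 0.20, 0.20, 0.25, 0.40, 0.70 and 0.70 for hospitals 1 to 6, with a within-hospital SD of 0.15. The control event rate is 20% at hospitals 1 to 4. The true effect of the mediator on outcome is zero. No patient covariates are modelled, so hospital's association with outcome stands for what remains after adjustment.

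**Large-sample coefficient without hospital.** Let g be the excess event rate at hospitals 5 and 6, averaged over arms.

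- Mean share = (3763×0.20 + 935×0.25 + 503×0.40 + 830×0.70)/6031 = 1768.55/6031 = 0.293.
- Between-hospital variance of the share = 0.0294; within-hospital variance = 0.15² = 0.0225; total = 0.0519.
- Covariance of share and outcome = g × 0.138 × (0.70 − 0.293) = 0.056g.
- Spurious mediator coefficient = 0.056g/0.0519 = 1.08g.
- Spurious indirect effect = (alert shift in mediator) × 1.08g. It is zero if the shift is zero or if g is zero.

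**Case A: baseline gap of 5 points.** With g = 0.05 and a shift of 0.05, the coefficient is 0.054 and the indirect effect 0.0027. Simulation gave 0.057 and 0.0027; confining the share to 0–1 accounts for the small difference.

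**Case B: equal control rates, alert effect of +8 points at hospitals 5 and 6 only.** Averaged over two equal arms, g = 0.08/2 = 0.04. With a shift of 0.05 the indirect effect is 0.05 × 1.08 × 0.04 = 0.0022. The pooled alert effect is 0.08 × 0.138 = 0.0110, so about 20% of it (0.0022/0.0110) would be wrongly called mediated.

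**How often a Sobel test at the 5% level declares mediation** (linear models, 300 or 400 runs per scenario where recorded, all six hospitals pooled):

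| Scenario | Shift | Without hospital | With hospital |
|---|---|---|---|
| Equal rates, no alert effect | 0.05 | 7.0% | 5.3% |
| Baseline gap 2 points | 0.05 | 11.5% | 3.3% |
| Baseline gap 5 points | 0.05 | 61.8% | 5.0% |
| Baseline gap 5 points | 0.02 | 45.5% | 3.5% |
| Baseline gap 5 points | 0 | 0.5% | 0.0% |
| Alert +8 points at 5–6 only, equal control rates | 0.05 | 42% and 48% (two sets of runs) | 6% and 4% |
| Alert +8 points at 5–6 only, equal control rates | 0.02 | 26% | 1% |
| Alert +4 points at 5–6 only, equal control rates | 0.05 | 13% | 4% |
| Alert +8 points at 5–6, plus baseline gap 5 points | 0.05 | 99% | 4% to 5% |

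**Direction.** A baseline gap of −4 points with the +8-point effect gives g = −0.04 + 0.04 = 0, so the bias cancels. A larger negative gap reverses its sign.

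**Hospitals 5 and 6 only.** With a shift of 0.05, false mediation was about 3% to 9% without hospital and 3% to 5% with it, near the nominal level.

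**The case against.** The strongest reply is that the SAP introduces this analysis because of harm at non-teaching hospitals and then asks what mediated that effect. A natural reading is that only hospitals 5 and 6 were analysed. They share personnel and have 1 and 0 trainees, so the staffing contrast behind the argument largely disappears. That stands: on this reading the omission matters little. But the text does not settle the population, and that is itself worth correcting.

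Second, a reader might infer that mediators and event rates do differ between hospitals, and that any mediation found is therefore spurious. The documents do not support this. They print neither quantity by hospital. They report heterogeneity of the alert effect, which is not a difference in baseline risk. The severity scores in Box 1 are close (SOFA medians 2, 1, 2, 2, 2, 2; Elixhauser medians 6, 6, 7, 6, 7, 7), and both scores are already in the model. For attending share, the trainee counts make a hospital difference a strong inference. For renal consult, medications and alert burden it is only a possibility.

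Third, nothing shows that the alert changed the attending share. With no shift there is essentially no spurious indirect effect. This too stands, as a condition on the point.

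Finally, the analysis is labelled post hoc, and the SAP warns that inferences from its unadjusted intervals may not be reproducible. That limits the consequence. It does not explain why hospital was left out of this one list.

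**Conclusion.** The omission is plain on the text and departs from the SAP's own practice elsewhere, with no reason given. It can create false mediation only if hospitals were pooled, the alert shifts the mediator, and hospital predicts outcome after the 16 patient covariates. An alert effect confined to hospitals 5 and 6 would itself supply the last condition in a model with a single alert term.

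Under the assumed inputs, pooled false mediation ranges from near nominal to almost certain, and hospital indicators bring it back to about 5% or below. Apart from enrolment, those inputs are assumptions. The figures show that the mechanism can matter; they do not estimate what happened in this trial, and even the sign is open.

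It would be wrong to conclude that the mediation results are false, or that the primary comparison, the per-hospital effects or the harm signal are in doubt. None of those depends on this model.

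**What to change.** State which hospitals entered the mediation analysis. Add hospital indicators to both the mediator model and the outcome model. The outcome model is where they remove bias; in the mediator model they mainly sharpen the estimate. If hospitals were pooled, also let the alert effect differ by hospital type, or run the analysis within hospital type.

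The cost is up to five degrees of freedom for six hospitals, plus any interaction term. For a mediator that nearly coincides with hospital, such as attending share, the indicators will also absorb much of its variation and widen the interval. Under the assumed shares, 0.0294/0.0519 = 57% of its variance lies between hospitals. That loss is real and should be reported, since it shows how little within-hospital information there is on that mediator.

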The primary analysis will utilize the intention to treat principle. The primary outcome (a composite of progression of AKI, dialysis, and death) will be compared across the groups using the Mantel-Haenszel chi-square test for correction for the 6 study strata (by hospital). Statistical significance will be based on a p-value of <0.05.

In addition, a retrospective examination will be performed to assess improvement in the control group before / after intervention as a measurement of contamination. We expect that providers who receive AKI alerts on some patients may be more likely to look for AKI in other patients, potentially diluting the effect of the intervention – this pre/post intervention analysis will help in assessing that level of contamination.

Because we are enrolling patients across six sites, we will do an exploratory analysis to determine the efficacy of alerts independently at each hospital.

We have specified several subgroups in whom the benefit of an AKI alert may differ from the general population. These groups will be analyzed as secondary and exploratory analyses. They include:

- Surgical patients
- Subjects with baseline creatinine <1.0mg/dl
- Subjects with baseline creatinine <0.5 mg/dl
- Females (due to lower rate of increase in creatinine after AKI)
- African Americans (due to higher rate of increase in creatinine after AKI)
- Elderly subjects (age > 65, age > 70, and age > 75)
- Subjects in an ICU at the time of the alert
- Subjects who enter the study based on relative vs. absolute creatinine criteria vs. both

Finally, as the academic year progresses, new clinicians (such as residents and interns) may become more facile in their ability to recognize AKI, which may attenuate the effect of this intervention. We will model this in exploratory analyses using an intervention-by-time of year interaction term in models of the primary outcome.

4. Genetic Testing N/A

A. Describe

- i. the types of future research to be conducted using the materials, specifying if immortalization of cell lines, whole exome or genome sequencing, genome wide association studies, or animal studies are planned
 - ii. the plan for the collection of material or the conditions under which material will be received
 - iii. the types of information about the donor/individual contributors that will be entered into a database
 - iv. the methods to uphold confidentiality

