alert except “dismiss”, the alert would be suppressed for 48 hours for that particular provider. If multiple providers used the EHR to care for the same patient, each of them separately received the AKI alert when they opened the patient chart. Patients randomized to the usual care group generated “silent” alerts which did not display to providers but were tracked, allowing the study team to observe which types of providers opened the chart and how often.

The alert contained an option to add AKI to the patient’s problem list, as well as a link to an AKI order set (Supplemental Figure S2); the set included options for blood and urine testing and renal imaging, but were limited to tests and procedures considered minimal risk (ie IV fluid administration was not included). Providers at each of the study hospitals received education regarding AKI and the AKI alert system prior to study rollout during departmental conferences. Educational content was standardized and included the following elements: the definition and clinical relevance of AKI, the rates of best practice completion after AKI has developed, the study design, and how to interact with the alert (specifically focusing on the consequences of “accepting” or “disagreeing” with the alert. There was no formal curriculum on how to treat AKI in various situations, but providers were reminded of best practices such as urinalysis, urine output monitoring, AKI documentation, and subsequent creatinine measurement.

The development of the alert was an iterative process which used focus groups of providers to give feedback on design elements and wording as well as incorporating suggestions from the IRB. Providers were asked what relevant information should be shown in the alert, what responses could be given, and what elements should appear in the AKI order set (although, due to IRB restrictions, no drug or fluid interventions could be included). They were also asked about alert behavior such as the appropriate “lockout” – how long the alert should be repressed after a provider interacts with it. The final alert was presented to our local Best Practice Alert committee who provided formal approval. The alert was then piloted in “silent mode” for several months for quality assurance. During this time, no

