alerts were displayed, but patient data was captured to ensure they met the inclusion / exclusion criteria and to gather data around alert frequency. Once the system was demonstrated to be working correctly, with approval from the BPA committee, the trial was started.

Outcome Measures

The primary outcome was a composite of inpatient AKI progression, receipt of dialysis, or death within 14 days of randomization. AKI progression was defined as reaching a KDIGO creatinine stage higher than the stage present at randomization. Stages 2 and 3 AKI are defined as an increase in creatinine level by 2–2.9 times and an increase ≥ 3 times baseline, respectively. Receipt of dialysis was also considered to be AKI progression. Patients discharged in the 14-day outcome period were assumed to not meet any of these outcomes had they not met them at the time of discharge. Pre-specified secondary outcomes included the components of the primary outcomes and rates of various AKI care practices. These practices included administration of contrast, fluids, or a nephrotoxic agent (an NSAID, ACE inhibitor / angiotensin receptor blocker or aminoglycoside), ordering of a urinalysis, documentation of AKI, monitoring of creatinine and urine output, and ordering for a kidney consult. An assessment of per-hospital alert effects was also pre-specified.

Data Collection

Data were collected electronically from the electronic health record using a centralized data warehouse (Joint Data Analytics Team, Yale New Haven Health System). Data collected included admission characteristics, time-updated hospital location, laboratory data, medication exposures, vital signs, comorbidities (based on ICD-10 administrative coding) and hospital disposition. Cost information was obtained from a separate database. Direct costs reflect those associated with direct patient contact involving billable services (for example lab, nursing costs, and supplies). Total costs also include non-

billable support services such as medical records, human resources, accounting, support staff, utilities and dietary costs.

Statistical Analysis

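### The before/after contamination check states no adjustment for calendar trend, case-mix or pre-rollout education, and it leaves out care practices

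*SAP*

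**What the plan says.** The protocol (Statistical Methods, repeated under item 12, Statistical Considerations) announces that "a retrospective examination will be performed to assess improvement in the control group before / after intervention as a measurement of contamination". Its reason is that "providers who receive AKI alerts on some patients may be more likely to look for AKI in other patients". It names no measure and no adjustment for this comparison.

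The SAP (Statistical Analysis) names the measure: death and AKI progression "in the time period 2 years prior to the start of the trial in each hospital", taken "to assess the degree of contamination across the study arms". No model, covariate or time term is given. In the same section the SAP lists covariates in full for the adjusted sensitivity analysis and for the mediation analysis.

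Three other statements bear on the point:

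- SAP, Intervention: "Providers at each of the study hospitals received education regarding AKI and the AKI alert system prior to study rollout". The content included reminders of urinalysis, urine output monitoring, documentation and repeat creatinine.
- SAP, Statistical Analysis (sample size paragraph): contamination is described as clinicians getting better at spotting and treating AKI as the trial goes on.
- SAP, Outcome Measures: rates of AKI care practices are pre-specified secondary outcomes. The contamination check does not mention them.

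**The concern.** A before/after change in the control group has several possible sources: calendar trend in AKI outcomes, a shift in case-mix, the education delivered before the first alert fired, and contamination. Only the last is the target. The education effect is a different quantity from the SAP's own notion of contamination, which builds up during the trial. Without terms for the other sources, the change cannot be assigned to any one of them.

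The choice of measure adds to this. The protocol's mechanism is that providers look for AKI in other patients. That would show first in documentation, urinalysis, repeat creatinine and consults, and only later, if at all, in death and progression.

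At stake is how the reader interprets a small between-arm difference. The planned enrolment was raised by about 1,000 patients on account of contamination, so the plan treats it as a serious possibility. An analysis that can show or hide contamination through trend alone is weak support for either reading.

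**Working it through.** **Inputs from the documents.** Composite rate 24.5%; target 19.6%; 5,024 patients before inflation and 6,030 after (Protocol, Sample Size Determination; SAP, Statistical Analysis). Pre-period of 2 years (SAP). Three years for enrolment, data acquisition and outcome assessment together (Protocol, Sample Size Determination).

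**The plan's own figures.** 24.5% × 0.80 = 19.6%, a design effect of 24.5 − 19.6 = 4.9 points. 5,024 × 1.20 = 6,028.8, stated as 6,030; the increase is 6,030 − 5,024 = 1,006 patients. The contamination check has no figure of its own. How 2,512 per arm was obtained is a separate question, and nothing here depends on it.

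**What the difference contains.** Let T be the trend per year, g the years between period midpoints, E the combined shift from education and case-mix, D the alert's absolute reduction in the outcome, and c the share of D that reaches control patients. The expected change in the control rate is

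Δ = g·T + E − c·D.

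One observed Δ cannot separate the three terms.

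**Gap between midpoints.** The pre-period midpoint lies 1.0 year before the start. If enrolment fills all three years, its midpoint is 1.5 years after, so g = 2.5. The three years also cover data acquisition and outcome assessment; if enrolment took two of them (an assumption), g = 1.0 + 1.0 = 2.0.

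**Drift alone (E = 0, c = 0).** The documents give no trend, so T is assumed. Each cell is g·T in points, with g·T / 4.9 in brackets.

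| Assumed trend, points/year | g = 2.0 | g = 2.5 |
|---|---|---|
| 0.5 | 1.00 (20%) | 1.25 (26%) |
| 1.0 | 2.00 (41%) | 2.50 (51%) |
| 1.5 | 3.00 (61%) | 3.75 (77%) |

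**Both directions of error.** With D = 4.9, contamination of c = 20% lowers the control rate by 0.20 × 4.9 = 0.98 points. A fall of 0.4 points/year over 2.5 years is 1.0 point and looks the same. In the other direction, c = 50% with a rise of 1 point/year gives 2.5 − 2.45 = +0.05 points, so substantial contamination is hidden.

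**Education alone.** An assumed effect of 1 or 2 points with c = 0 looks like 1/4.9 = 20% or 2/4.9 = 41% contamination.

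**If the alert does not change outcomes (D = 0).** Then c·D = 0 and Δ carries no information on c. The between-arm difference in the primary outcome is (1 − c)·D, which is also zero for every c, so contamination does no damage there. For a care practice that the alert changes by P, the between-arm difference is (1 − c)·P. Contamination still shrinks that, and an outcome-only check cannot show it.

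**The case against.** The strongest reply has four parts.

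1. **A reader might infer that the check fails because it cannot detect contamination when the alert has no effect on outcomes, so that a null primary result could not be interpreted.** The documents do not support this. With no outcome effect, contamination cannot dilute the primary outcome either, and a null is then a correct null. The SAP's worry is bias towards the null, and outcomes are a relevant scale for that. What remains is the dilution of the care-practice comparisons.
2. **A reader might infer that this is the plan's only means of telling an ineffective alert from a diluted one.** It is not. The SAP also fits an interaction of randomized assignment with time since first enrolment at the hospital. That is a within-trial comparison, largely free of pre-trial trend, and it addresses learning that accumulates. It is partial: it needs an outcome effect, and it would miss contamination that was complete at the start.
3. **Unadjusted is an inference.** The SAP says only that rates were examined, and the protocol says that the analysis will help in assessing contamination. No test or decision rule is attached. This stands; the point is that no adjustment is stated, not that one was ruled out.
4. **The size rests on assumptions.** This also stands. The documents contain no trend, and the gap depends on how much of the three years was enrolment.

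Care practices are already compared between arms, but that comparison is itself diluted by contamination and so cannot measure it. Practice in the usual-care arm over time is what is missing.

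**Conclusion.** The point holds as a minor improvement to a supporting analysis. As described, the before/after difference mixes contamination with calendar trend, case-mix and pre-rollout education, and it omits the practices where contamination would first appear. For assumed trends of 0.5 to 1.5 points per year and gaps of 2.0 to 2.5 years, drift alone would be 1.0 to 3.75 points, or 20–77% of the 4.9-point design effect. These are illustrations of sensitivity; the documents do not show that such a trend occurred.

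The randomized primary comparison is not affected. If the alert changes outcomes strongly and drift is small, the existing check has some value.

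**What to change.** Compare usual-care patients with pre-trial patients found by the same algorithm, in a model with hospital, calendar-time trend, case-mix and a step at each hospital's go-live date. Pool across hospitals where sites are small: Hospital 6 enrolled 146 patients over both arms (SAP, Box 1).

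Apply the model to AKI documentation, urinalysis, repeat creatinine and renal consult as well as to outcomes, where the warehouse holds these for the pre-period. The silent-mode months are a natural part of the pre-period. The SAP says that "patient data was captured to ensure they met the inclusion / exclusion criteria" and to study alert frequency, so whether practice measures exist for those months must be checked.

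Report the slope of practice in the usual-care arm after go-live, and read it alongside the alert-by-time interaction. State that the unadjusted before/after difference does not by itself measure contamination.

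The cost is analysis work only. No linkage to individual clinicians is needed, so the protocol's commitment on that (Subject Recruitment and Screening) is kept. The downsides are wider intervals and a step that still combines education with early contamination. The periodic teaching during the trial (Protocol, Blinding of Intervention) may also enter the slope.
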